### 23.3. Treatment of Missing and Spurious Data

Spurious data, which were not clarified by the query process before CDMS closure, are indicated. If appropriate, descriptive and inferential analyses are performed both with /without such data.

#### 23.1. Exclusion of Particular Information

No data from the previous defined analysis set are excluded from the analysis except those defined in chapter 5.5, if applicable.

#### 23.2. Descriptive Analyses

If applicable, mean and median survival times are presented by using the Kaplan-Meier estimates. Kaplan-Meier survival figures are presented for illustration.

Other descriptive data will be presented via tables as specified in chapter 5.1.

#### 23.3. Hypotheses & Statistical Tests

Differences of the survival curves BioMonitor versus control group are tested for statistical inference with the log-rank test.

The hazard ratio for the BioMonitor versus control group including 95%CI is calculated with the Cox regression model. In case of doubt about the validity of the Cox model, the assumption of proportional hazards is checked graphically by log-minus-log survival versus log-time plots.

## 24. Other sec. EP: Quality of Life / WHO-5 Well-being Index

### 24.1. Analysis set

This endpoint is analyzed exclusively for the final statistical analysis report based on the ITT analysis set.

### 24.2. Variables

#### *CIP Chapter 8.3.3.12 Quality of Life (QoL)*

*A further secondary endpoint is the assessment of the patient's quality of life. The patient's quality of life will be recorded during the regular telephone contacts using the WHO-5 Well-being Index.*

Data file: Identifier record_ID	Notes	Variable name	Variable label	Variable level	Nominal values
who_five_well_being_index	No report	interview_interval	Interval (filled in automatically)	nominal	1. Quality of Life (6 M) 2. Quality of Life (12 M) 3. Quality of Life (18 M) 4. Quality of Life (24 M) 5. Quality of Life (30 M) 6. Quality of Life (36 M) 7. Quality of Life (42 M) 8. Quality of Life (48 M) 9. Quality of Life (54 M) 10. Quality of Life (60 M)
		q1_multi	I have felt cheerful and good spirits	ordinal	0,1,2,3,4,5
		q2_multi	I have felt calm and relaxed	ordinal	0,1,2,3,4,5
		q3_multi	I have felt active and vigorous	ordinal	0,1,2,3,4,5
		q4_multi	I woke up feeling fresh and rested	ordinal	0,1,2,3,4,5
		q5_multi	My daily life has been filled with things that interest me	ordinal	0,1,2,3,4,5

Data file: Identifier	Notes	Variable name	Variable label	Variable level	Nominal values
patient_display_id_full					
data_SAR	descr.	wbi_percscore_6m_SAR 	WBI percentage score: 6m	scale	0-100
data_SAR	descr.	wbi_percscore_12m_SAR 	WBI percentage score: 12m	scale	0-100
data_SAR	descr.	wbi_percscore_18m_SAR 	WBI percentage score: 18m	scale	0-100
data_SAR	descr.	wbi_percscore_24m_SAR 	WBI percentage score: 24m	scale	0-100
data_SAR	descr.	wbi_percscore_30m_SAR 	WBI percentage score: 30m	scale	0-100
data_SAR	descr.	wbi_percscore_36m_SAR 	WBI percentage score: 36m	scale	0-100
data_SAR	descr.	wbi_percscore_42m_SAR 	WBI percentage score: 42m	scale	0-100
data_SAR	descr.	wbi_percscore_48m_SAR 	WBI percentage score: 48m	scale	0-100
data_SAR	descr.	wbi_percscore_54m_SAR 	WBI percentage score: 54m	scale	0-100
data_SAR	descr.	wbi_percscore_60m_SAR 	WBI percentage score: 60m	scale	0-100
data_SAR	descr.	wbi_percscore_24m_6m_SAR 	WBI percentage score: Difference 24m vs. 6m	scale	-100 till 100
data_SAR	descr.	wbi_percscore_48m_6m_SAR 	WBI percentage score: Difference 48m vs. 6m	scale	-100 till 100

### 24.3. Treatment of Missing and Spurious Data

Spurious data, which were not clarified by the query process before CDMS closure, are indicated. If appropriate, descriptive and inferential analyses are performed both with /without such data.

Missing data from a specific in hospital follow-up is imputed with the Last-Observation-Carry-Forward method, i.e. data from the nearest previous in-hospital follow-up, if available.

#### 24.1. Exclusion of Particular Information

No data from the previous defined analysis set are excluded from the analysis except those defined in chapter 5.5, if applicable.

#### 24.2. Descriptive Analyses

Descriptive data are presented via tables as specified in chapter 5.1.

### 24.3. Hypotheses & Statistical Tests

The percentage Well-Being Index for the 6m in-hospital FU, 24m in-hospital FU, 48m in-hospital FU, differences between 24m and 6m, and differences between 48m and 6m are analyzed BioMonitor versus control group with the Mann-Whitney-U test.

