### **Follow-up**

- No pre-planned in-hospital follow-up visits  
Unplanned visits (patient- or investigator initiated) possible; reason for visit and treatment will be documented
- Initial telephone call at 4 weeks post-enrollment
- Telephone contact every 6 months using a questionnaire with focus on endpoint-related data as well as questionnaires covering quality of life aspects (WHO-5 Well-being Index and EQ-5D-5L questionnaire)

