#### 7.1.3.12 Quality of Life (QoL)

The investigation of the patients' quality of life is not intended to show a benefit by the implantation of the ICM, but to exclude that the implantation or the monitoring of patients has a negative impact on their well-being.

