## 9.6 Telephone follow-up

A telephone follow-up regimen will be implemented and replace in-hospital follow-up visits. To obtain endpoint related information, all patients will receive telephone calls once 4 weeks after enrollment and then every 6 months where they will be asked to answer a study specific questionnaire. In addition, the patient's quality of life will be assessed using the WHO-5 Well-being Index.

The Index was chosen for its:

- Focus on the emotional well being of the patient
- Applicability during a telephone contact

In addition, the EQ-5D-5L questionnaire will be administered during the telephone contacts to gather outcome data for an economic evaluation.

About the EQ-5D-5L:

- The EQ-5D-5L instrument consists of two distinct elements: the EQ-5D descriptive classification system and the EQ visual analogue scale (EQ VAS).

- The descriptive classification system comprises five dimensions: mobility, self-care, usual activities, pain/discomfort and anxiety/depression. Each dimension has 5 levels: no problems, slight problems, moderate problems, severe problems and extreme problems.
- The patient is asked to indicate his/her general health state by indicating the most appropriate statement for each of the five dimensions, with each decision resulting in a 1-digit number that expresses the level selected for that dimension. The digits for the five dimensions can then be combined into a 5-digit number that describes the patient's health state. Valuation sets are available for various countries which can then be used to estimate quality-adjusted life-years (QALYs).
- The EQ VAS records the patient's self-rated health on a vertical visual analogue scale, where the endpoints are labelled 'The best health you can imagine' and 'The worst health you can imagine'. The VAS can be used as a quantitative measure of health outcome that reflects the patient's own judgement on the day of measurement.

Telephonic follow-up activities and consequent source data tracking will be performed by an external CRO contracted by the sponsor (see section 9.8.6). Detailed telephone follow-up guidelines will be provided in a separate document, the 'telephone follow-up manual'.

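### WHO-5 is scored at ten calls but tested only at 6, 24 and 48 months, by rank tests with LOCF and no effect estimate or confidence interval, so the planned tests cannot meet the aim of excluding harm to well-being

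*SAP*

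**What the plan says.** **Aim.** Protocol 7.1.3.12 says the quality-of-life assessment is not meant to show a benefit of the device but "to exclude that the implantation or the monitoring of patients has a negative impact on their well-being". Protocol 7.3 defines no hypothesis for this objective and leaves the details to the SAP. Neither document gives a margin.

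**Collection.** Under Protocol 9.6, "all patients will receive telephone calls once 4 weeks after enrollment and then every 6 months". SAP 24.2 (Variables) lists WHO-5 intervals from 6 to 60 months in steps of six and derives ten scores, for example "WBI percentage score: 12m". It lists no WHO-5 baseline, whereas the EQ-5D-5L list in SAP 25.2 has one.

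**Tests.** SAP 24.3 (Hypotheses & Statistical Tests) names "The percentage Well-Being Index for the 6m in-hospital FU, 24m in-hospital FU, 48m in-hospital FU", and adds that "differences between 24m and 6m, and differences between 48m and 6m are analyzed BioMonitor versus control group with the Mann-Whitney-U test". That makes five tests built from three time points. No longitudinal model, arm difference or confidence interval is planned.

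**Other handling.** All ten scores are marked for description and presented in the SAP 5.1 tables, whose model layouts include one split by randomised group. SAP 24.3 (Treatment of Missing and Spurious Data) imputes a missing score by last observation carried forward (LOCF).

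**The concern.** An aim of excluding harm is met by an interval for the arm difference that rules out a harm of relevant size. The plan gives five p-values instead. A non-significant result may mean no harm or too little information, and the reader could not tell which. The time-to-event secondary endpoints in SAP 12 to 21 and 23 each get a hazard ratio with a 95% interval; WHO-5 gets no counterpart.

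The choice of time points adds to this. Scores at 12, 18, 30, 36, 42, 54 and 60 months have no test of their own, although they are collected and bear on the same question. A fall at 12 to 18 months would appear only in descriptive tables, unless LOCF happened to carry a score into the 24-month test.

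**Working it through.** **1. The plan's own figure.** There is none for WHO-5: no standard deviation, power, margin or expected precision is stated. The calculation below therefore compares analyses; the standard deviation cancels.

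**2. Time points.** Derived: 6, 12, 18, 24, 30, 36, 42, 48, 54, 60 months (10). Tested: 6, 24, 48 (3). The two change scores use the same three. Without a test of their own: 10 − 3 = 7.

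**3. Share of collected scores.** Assumptions: uniform entry over 36 to 66 months and 0 to 20% missed calls. From the protocol: a 74-month study and 5% drop-out a year. Then 33 to 36% of collected scores fall at 6, 24 or 48 months, leaving 64 to 67% outside the tests. If LOCF fills every missing 24- and 48-month value for which an earlier score exists, 37 to 50% enter a test and about 50 to 63% still do not.

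**4. Precision.** Assumptions: equal variances, the same within-patient correlation ρ between any two calls, complete scores, and an arm difference roughly constant over time. The variance of a mean of k calls relative to one call is

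v(k) = ρ + (1 − ρ)/k.

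| ρ | v(2) | v(4) | SE, 4 calls vs 1: √v(4) | SE, 4 calls vs 2: √(v(4)/v(2)) | Patient equivalent vs 2: v(2)/v(4) |
|---|---|---|---|---|---|
| 0.5 | 0.750 | 0.625 | 0.79 | 0.913 | 1.20 |
| 0.6 | 0.800 | 0.700 | 0.84 | 0.935 | 1.14 |
| 0.7 | 0.850 | 0.775 | 0.88 | 0.955 | 1.10 |

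The four calls are 6, 12, 18 and 24 months; the two are 6 and 24 months, both already tested. Against one visit the standard error is 12 to 21% smaller. Against the mean of the two tested visits it is about 4 to 9% smaller, equal to about 10 to 20% more patients.

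Over the full schedule, the ratio for ten calls against the three tested, √(v(10)/v(3)), is 0.91 at ρ = 0.5 and 0.955 at ρ = 0.7. Over ρ from 0.4 to 0.8 it runs from 0.88 to 0.97.

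**5. What LOCF does to the change scores.** If a patient's only score is at 6 months, the carried-forward 24-month value equals it and the 24-minus-6 change is exactly zero. The same holds at 48 months. Such zeros pull both arms towards no change, an unhelpful direction when harm is to be excluded.

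**6. The 48-month tests.** SAP 5.7 dates the announcement of phase 2 to June 2018, and the protocol targets last patient out for about October 2021, some 40 months later. On that timeline a patient enrolled after the announcement cannot have an observed 48-month score. That includes every US patient, since Protocol 23.1 has the US join only in phase 2. They can enter the two 48-month tests only through a carried-forward value.

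**The case against.** Much of the opposing case is sound.

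- **A reader might infer that seven time points are compared nowhere.** The documents do not support that. All ten scores are tabulated, and the model layouts in SAP 5.1 include a split by arm. LOCF also moves some intermediate scores into the 24- and 48-month tests. What is missing is a test of their own and an interval.
- **A reader might infer that a model rescues patients who missed the 24-month call and whom the plan would lose.** LOCF already brings them in if they have an earlier score. The model's advantage is that it uses their observed scores without inventing a value.
- **A reader might infer a gain worth 29 to 60% more patients** (1/0.775 to 1/0.625). That sets four visits against one, but two of the four are already tested. Much of that gain comes from pooling tested visits; the untested calls add the 10 to 20% shown above.
- **An average can hide a transient effect.** A fall confined to 12 and 18 months is halved in a 6-to-24-month average and cut to one fifth in an equally weighted average of ten calls. This stands, and it is why differences at each visit must be reported as well. With complete data the model adds no precision to those.
- **Pre-selecting three time points limits the number of tests**, SAP 5.2 chooses rank tests for all metric data for comparability, and Protocol 11.5 rests pass or fail on the primary hypothesis alone. This is fair and limits the weight of the point. It does not explain how rank tests without an interval could exclude harm.
- **SAP 1.4 states that all persons responsible for SAP 3.0 were unblinded.** A new main analysis or a hand-picked time window could look data-driven. This stands and shapes the fix.

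**Conclusion.** The concern holds in limited form. As planned, the WHO-5 analysis cannot answer the protocol's question, because five Mann-Whitney tests with no estimate, interval or margin cannot exclude a negative effect. The secondary fault is lost precision, and it is modest: about 4 to 9% in standard error over 6 to 24 months against the two visits already tested. That figure rests on an assumed correlation of 0.5 to 0.7, equal correlation between calls, complete scores and a roughly constant arm difference, none of which the documents give. Greater precision alone would not exclude harm either; the interval, and preferably a margin, is what makes the objective answerable. The primary endpoint is unaffected, so this is a worthwhile correction to a secondary analysis.

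**What to change.** In SAP 24.3 (Hypotheses & Statistical Tests), add a mixed model for repeated measures on all observed WHO-5 scores, without LOCF, with terms for arm, visit, arm by visit and STEMI/NSTEMI. Report the average arm difference over the scheduled calls, with the weighting of the calls fixed in the text, and the difference at each visit, each with a 95% confidence interval. State in words what size of harm the intervals exclude, ideally against a margin set in advance. Keep the planned Mann-Whitney tests. In the same edit, reconcile the in-hospital follow-up wording in both sections numbered 24.3 with the telephone collection in Protocol 9.6.

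The cost is a few lines of SAP text and one model on data already collected. There are three downsides. The model assumes data missing at random, so scores absent because of death need explicit comment. It assumes approximate normality of a 0 to 100 score, for which the retained rank tests are a check. And because of the unblinding in SAP 1.4, the addition must be dated, justified and labelled as made after unblinding.

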### 7.3 Secondary hypotheses

The objective to show that arrhythmias requiring guideline-recommended therapy will be detected earlier in the BioMonitor group will be formally tested similarly to the primary hypothesis. The HR is defined as the rate of the BioMonitor group divided by the rate of the control group.

H0: Null hypothesis:  $H_0 : HR \leq 1$

which means that monitoring patients of the BioMonitor group will *not* lead to a shorter time to first arrhythmia that requires guideline-recommended therapy, in the BioMonitor group compared to the control group.

HA: Alternative hypothesis:  $H_A : HR > 1$

which means that monitoring patients of the BioMonitor group will lead to a shorter time to first arrhythmia that requires guideline-recommended therapy compared to the control group.

It is expected that there is a  $HR > 1$  for the BioMonitor group. A rejection of the null hypothesis indicates that arrhythmias are detected earlier in the BioMonitor group.

No hypotheses have been pre-defined for the other secondary objectives. Details will be specified in a separate Statistical Analysis Plan (SAP).

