#### 8.3.3.12 Quality of Life (QoL)

A further secondary endpoint is the assessment of the patient's quality of life. The patient's quality of life will be recorded during the regular telephone contacts using the WHO-5 Well-being Index.

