### 14.6. Hypotheses & Statistical Tests

Differences of the survival curves BioMonitor versus control group are tested for statistical inference with the log-rank test.

The hazard ratio for the BioMonitor versus control group including 95%CI is calculated with the Cox regression model. In case of doubt about the validity of the Cox model, the assumption of proportional hazards is checked graphically by log-minus-log survival versus log-time plots.

## 15. Other sec. EP: Time to 1st worsening of the patient status due to heart failure ...

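### The WHO-5 objective is to exclude harm to well-being, but the SAP plans no estimate or interval for the arm difference, and its visible LOCF rule names the wrong type of contact and leaves its scope open

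*SAP*

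**What the plan says.** - **Objective.** Protocol 7.1.3.12 says quality of life is not studied to show a benefit, but "to exclude that the implantation or the monitoring of patients has a negative impact on their well-being".
- **Hypothesis.** Protocol 7.3 states: "No hypotheses have been pre-defined for the other secondary objectives". It leaves details to the SAP.
- **Tests.** SAP 24.3 (Hypotheses & Statistical Tests) compares the arms on the WHO-5 percentage score at 6, 24 and 48 months. It adds that "differences between 24m and 6m, and differences between 48m and 6m are analyzed BioMonitor versus control group with the Mann-Whitney-U test".
- **Other output.** SAP 24.2 (Descriptive Analyses) says: "Descriptive data are presented via tables as specified in chapter 5.1". The chapter 5.1 template for metric data gives N, mean, SD, range and quartiles by arm, with no arm difference.
- **Contrast.** For the time-to-event secondary endpoints the SAP plans an effect estimate with an interval. In SAP 14.6, for example: "The hazard ratio for the BioMonitor versus control group including 95%CI is calculated with the Cox regression model".
- **Missing scores.** SAP 24.3 (Treatment of Missing and Spurious Data) says: "Missing data from a specific in hospital follow-up is imputed with the Last-Observation-Carry-Forward method". The value comes from the nearest previous in-hospital follow-up.
- **Collection.** Protocol 8.3.3.12 says the score is "recorded during the regular telephone contacts using the WHO-5 Well-being Index", and Protocol 9.6 says: "A telephone follow-up regimen will be implemented and replace in-hospital follow-up visits".

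**The concern.** Excluding harm means putting a bound on the arm difference. A test of no difference does not give one: a non-significant result can come from a negligible effect or from too few scores. The SAP supplies such a bound for its time-to-event secondary endpoints but not for the one endpoint whose stated purpose is to rule out harm. As planned, the WHO-5 results could not support a statement that monitoring leaves well-being unharmed.

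The LOCF rule is a smaller problem. Read literally it fills nothing, because scores are not collected at in-hospital visits. The label probably means the 6-monthly call, since the tests in the same chapter also call the scores in-hospital. On that reading the visible text still does not say whether LOCF fills only missed calls, or also calls after drop-out, or calls not yet due when the study closes. Carrying early scores forward dilutes an effect that emerges late, by an amount that depends on the answer.

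**Working it through.** The documents give no sample size, SD or margin for the WHO-5, so there is no plan figure to reproduce. The figures below are illustrations.

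**From the documents**
- Drop-out 5% per year (Protocol 11.4).
- First phase of 640 patients in about 24 months (Protocol 8.1); ceiling of 2900 (Protocol 8.9.1).
- August 2015 to about October 2021, 74 months (Protocol 8.9.6). A 48-month call therefore needs entry by month 26, and a 24-month call by month 50.

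**Assumed**
- Total enrolled N = 1000 to 2900. The first 640 enter evenly over months 0 to 24 and the rest evenly over months 24 to 66.
- SD 18 to 25 points, a true harm of 5 points, a two-sided 5% test and a normal approximation to the rank test.

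**Observed scores per arm**
- 48 months: [640 + (N − 640) × 2/42] × 0.95⁴ / 2. N = 1000: 657 × 0.8145 / 2 = 268. N = 2900: 748 × 0.8145 / 2 = 304.
- 48 months, slower accrual: SAP 5.7 dates the announcement of phase 2 to June 2018, month 34. This may reflect slower entry or only adjudication delay. With 640 entering over 34 months: 640 × 26/34 × 0.8145 / 2 = 199.
- 24 months: [640 + (N − 640) × 26/42] × 0.95² / 2. N = 1000: 389. N = 2900: 920.

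**Precision.** Half-width = 1.96 × SD × √(2/n). P(non-significant) = Φ(1.96 − 5 / [SD × √(2/n)]).

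| Time | n per arm | Half-width, SD 18 / 25 | 5-point harm missed, SD 18 / 25 |
|---|---|---|---|
| 48 m, N = 1000 | 268 | 3.0 / 4.2 | 10% / 36% |
| 48 m, N = 2900 | 304 | 2.9 / 4.0 | 7% / 31% |
| 48 m, slower accrual | 199 | 3.5 / 4.9 | 21% / 49% |
| 24 m, N = 1000 | 389 | 2.5 / 3.5 | 3% / 20% |
| 24 m, N = 2900 | 920 | 1.6 / 2.3 | under 1% / 1% |

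**Share of analysed 48-month scores carried forward, by LOCF scope**
- Missed calls of active patients only: about 0%, because missed calls beyond drop-out are not modelled.
- Also calls that fell due after drop-out: 1 − 0.95⁴ / 0.95^0.5 = 1 − 0.95^3.5 = 16%.
- Also calls not yet due: 1 − (share due × 0.8145) / 0.9747, where 0.9747 = 0.95^0.5 is the share with any score. The share due is 0.657, 0.454 and 0.258 for N = 1000, 1500 and 2900. The share carried is 45%, 62% and 78%.

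**The case against.** **The information is not lost.** The chapter 5.1 tables give N, mean and SD by arm, so a reader can form a mean difference and an approximate interval. That is true and limits the damage. But it is not a planned result, and a difference in means is not the effect measure that goes with a rank test.

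**No claim of no harm is announced.** A reader might infer that the sponsor will take a non-significant p-value as proof of no harm. The documents do not say so, and Protocol 7.3 pre-defines no hypothesis here. The point is only that the planned output does not address the stated objective.

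**The LOCF gap may not exist.** A reader might infer that scores are carried past death or that most 48-month values would be imputed. The visible text does not establish either. The derived WHO-5 variables carry footnotes 125 to 136, which are not shown and may define the scope. Protocol 8.9.5 ends participation on the date of death. A natural reading of the rule fills only missed calls of active patients, with little effect. The 45 to 78% end requires treating calls that never fell due as missing.

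**Replacing the analysis would be a preference.** SAP 5.2 chose rank tests for all metric data and gave a reason. SAP 1.4 reports that everyone responsible for version 3.0 was unblinded, so a new main analysis now would be a post-unblinding change. This stands: the remedy should add to the rank tests and not replace them.

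**Low priority.** This is an other secondary endpoint. Agreed, and the size of the request reflects that.

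**Conclusion.** The mismatch between objective and analysis holds on the visible text: the aim is to exclude harm, and the plan contains difference tests and per-arm summaries but no estimate or interval for the arm difference. At 48 months the interval would reach about 2.9 to 4.2 points either side, or 3.5 to 4.9 with slower accrual. A true 5-point harm would go undetected in about 7 to 36%, or 21 to 49%, of trials. At 24 months the figures are 1.6 to 3.5 points and under 1% to 20%. All of these rest on the assumed SD, harm, enrolment and accrual. The miss rates reflect sample size, which the fix does not change; they show why a non-significant p-value should not stand alone.

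The in-hospital label is wrong on the documents' own account of how scores are collected. That the LOCF scope is unstated holds only for the visible text; the carried share at 48 months could be anywhere from about 0% to 78%. The primary conclusion is not touched. The change is worth making because it is nearly free.

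**What to change.** In SAP 24:

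1. Beside each Mann-Whitney test, report the Hodges-Lehmann shift, BioMonitor minus control, with 95% CI and the number of observed scores per arm.
2. State that a non-significant p-value is not read as excluding harm. Make no claim of no negative impact unless a margin is justified by people without access to arm-level data.
3. Replace in-hospital follow-up with telephone contact in both places.
4. State that LOCF fills only calls that fell due in living, active patients. Show the same estimates on observed scores without LOCF.
5. Declare these as additions made after the unblinding described in SAP 1.4.

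A repeated-measures model is optional and supportive only.

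Cost: SAP wording and slightly more analysis work, with no new data. The observed-score intervals will be wider at 48 months.

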## 8 DESIGN OF THE CLINICAL INVESTIGATION

### 8.1 General considerations

The BIO|GUARD-MI study is a multicenter, prospective, randomized (1:1), controlled, parallel-group, open, international study (including USA) with an event-driven design. The study is operatively divided into 2 phases. In the first phase 640 patients will be enrolled within approximately 2 years after FPI. After 600 patient years of cumulative follow-up have been collected, a blinded analysis will be performed to assess the primary endpoint rate. Based on the assessed rate (see section 11.7), the study will enter the second phase or be discontinued prematurely. This is necessary because it is impossible to obtain solid estimates of the endpoint rates for the included population from the literature. In case of a too low endpoint rate, the study could be expected to fail in its primary objective, even if the BioMonitor group had a much reduced endpoint rate.

In the second phase enrollment will continue in the same way, but in more investigational sites than the first phase, and without interception until up to 2900 patients entered the study. The duration of the second study phase is estimated to last 4 years but ultimately is dependent on when the number of needed endpoints for the final analysis is reached. In the second phase US patients will contribute to the study.

As a result of the specific national requirements in the U.S., a U.S.-specific amended protocol is valid for U.S. sites. Differences compared to this Clinical Investigation Plan are displayed in section 23.1.

The study includes an enrollment-assessment and randomization procedure. The randomization is 1:1, either in the BioMonitor group (patients are implanted with the BioMonitor) or in the control group (patients do not receive a device). The qualifying measurement of the LVEF should be from the time after conclusion of the acute treatment of the most recent MI but not older than 6 months. For patients randomized to the BioMonitor group, the implantation shall be performed as soon as possible but at latest 8 weeks after enrollment. Most study procedures will typically take place during the index hospitalization (enrollment, implantation if applicable and discharge).

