### **8.9.6 Timelines**

[figure not shown]
First Patient In (FPI): Aug 2015 (actual date of FPI)

Last Patient Out (LPO): ~ Oct 2021 Total study duration: ~ 74 months

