### CIP chapter 11.7 Termination Criteria

There is a blinded evaluation of the MACE rates after the event-check, which is no interim analysis because no therapy effect is investigated. If the total number of patients with at least one MACE in both groups is less than 20 patients per 600 patient-years at the end of the event-check phase, the study will be terminated.

...

Via the Study News report, Issue 15 from June 2018, the investigators were informed that the gateway to study phase 2 has been reached. The EAEC Board evaluated 20 events as primary endpoint-related. Thus, phase 2 for the study was announced.

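### The 48-month WHO-5 tests cover the whole ITT set and, on the natural reading of the LOCF rule, count earlier scores as 48-month scores for patients who could never have a 48-month call

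*SAP*

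**What the plan says.** SAP 24.1 places the WHO-5 analysis on the ITT set, and the section on exclusions adds nothing beyond chapter 5.5. SAP 24.3 (Hypotheses & Statistical Tests) compares the arms at 6, 24 and 48 months and on two changes, 24 minus 6 months and 48 minus 6 months. Of the last it says that "differences between 48m and 6m are analyzed BioMonitor versus control group with the Mann-Whitney-U test".

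The other section numbered 24.3 (Treatment of Missing and Spurious Data) says that a missing score is "imputed with the Last-Observation-Carry-Forward method, i.e. data from the nearest previous in-hospital follow-up, if available". Both sections call the contacts in-hospital follow-ups. CIP 9.6 says that WHO-5 is collected by telephone, with calls 4 weeks after enrolment and then every 6 months, in place of in-hospital visits.

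The purpose of the endpoint, in CIP 7.1.3.12, is "to exclude that the implantation or the monitoring of patients has a negative impact on their well-being".

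The calendar is as follows. First patient in was August 2015, and CIP 8.9.6 gives "Last Patient Out (LPO): ~ Oct 2021 Total study duration: ~ 74 months". CIP 8.1 plans that "In the first phase 640 patients will be enrolled within approximately 2 years after FPI", with a total of up to 2900. SAP 5.7 records: "Via the Study News report, Issue 15 from June 2018, the investigators were informed that the gateway to study phase 2 has been reached". SAP 6.8 states that no patient's termination can fall after the formal end of the study.

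**The concern.** Follow-up ends on a common date, so a patient's longest possible follow-up depends on when that patient enrolled. A 48-month call can fall due only for early entrants. The analysis set and the missing-data rule do not distinguish a call that was missed from a call that could never take place.

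Applied as written, the rule would put a late entrant's 6- to 36-month score into the 48-month variable. A patient whose only score is at 6 months would get a 48-minus-6-month change of exactly zero. The result would be reported as a 48-month ITT comparison, although part of it describes much shorter follow-up.

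This matters because the stated aim is to rule out harm. Carrying early scores forward pulls the estimated difference towards zero when harm emerges late or accumulates. SAP 1.1 also makes the inferential analyses of the secondary endpoints mandatory in the final report.

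**Working it through.** **1. The plan's own figure.** August 2015 to October 2021 is 6 × 12 + 2 = 74 months, as stated in CIP 8.9.6.

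**2. Who can reach 48 months.**
- Latest enrolment for a 48-month call: October 2021 − 48 months = October 2017, month 74 − 48 = 26 after first patient in.
- Latest enrolment for a 24-month call: October 2019, month 50.
- June 2018 (month 34) to October 2021 is 74 − 34 = 40 months, so the last possible 6-monthly call is at 36 months. If the end slipped by 3 months there would be 43 months, still short of 48.

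**3. How many real 48-month scores.** Assumptions: 640 enrolled by October 2017 (the plan's phase 1 number, not a reported count) and 5% drop-out per year (CIP 11.4). Then 640 × 0.95⁴ ≈ 521. Total enrolment N is not stated, so it is varied. As a sensitivity case, if the 640 accrued evenly up to June 2018, then 640 × 26/34 ≈ 489 would have entered by October 2017, and 489 × 0.95⁴ ≈ 399 would remain.

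| N | 521 / N | 399 / N |
|---|---|---|
| 2900 | 18% | 14% |
| 1500 | 35% | 27% |
| 1000 | 52% | 40% |

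On the 521 figure, real scores fall below half of patients once N exceeds 521 / 0.5 ≈ 1,042.

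**4. How far a growing difference shrinks.** Assumptions: phase 1 entry uniform over months 0–24; phase 2 entry uniform from month 34 to month 62 or 68, or from month 24 to 68; 5% drop-out per year. The last completed call is the follow-up rounded down to a multiple of 6, capped at 48. If a difference grows linearly from 6 to 48 months, the fraction left after carrying forward is (mean true time − 6) / 42.

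| N | Phase 2 entry (months) | Mean true time of the 48-month value | Fraction left |
|---|---|---|---|
| 2900 | 34–68 | 24.8 | 18.8/42 = 45% |
| 2900 | 34–62 | 27.0 | 21.0/42 = 50% |
| 2900 | 24–68 | 28.2 | 22.2/42 = 53% |
| 1000 | 34–68 | 35.1 | 29.1/42 = 69% |
| 1000 | 34–62 | 36.1 | 30.1/42 = 72% |
| 1000 | 24–68 | 36.7 | 30.7/42 = 73% |

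The rows starting at month 24 use the nominal two-year phase 1, not the June 2018 date.

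**5. Effect on the test.** Simulation of 1,000 trials: Mann-Whitney test at two-sided 5%, true difference at 48 months 0.25 SD, within-patient correlation 0.6, phase 2 entry in months 34–68. SD, effect size and correlation are assumptions.

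| Pattern of harm | N | Estimated 48m difference with LOCF (SD) | Power 48m, observed only → LOCF | Power 48m−6m, observed only → LOCF |
|---|---|---|---|---|
| Only after 36 months | 2900 | 0.046 | 0.80 → 0.23 | 0.86 → 0.27 |
| Only after 36 months | 1000 | 0.14 | 0.81 → 0.56 | 0.87 → 0.69 |
| Linear from 6 months | 2900 | 0.11 | 0.80 → 0.83 | 0.87 → 0.93 |
| Linear from 6 months | 1000 | 0.17 | 0.80 → 0.76 | 0.87 → 0.86 |

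The estimate shrinks under both patterns. Power falls heavily only when the harm appears late.

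**The case against.** *The rule may not reach these calls.* A call that was never due need not count as missing, and read literally an in-hospital rule covers no telephone contact. Footnotes 125 to 136, which define the derived WHO-5 scores, are not in the text available here and could contain a restriction. This stands as a limit on certainty. However, the test section uses the same in-hospital label for the WHO-5 time points, so the natural reading is that the rule applies to them. If it does not, the 48-month test describes an early-enrolled subset. That subset would contain no U.S. patients on the June 2018 date, because U.S. sites join only in phase 2, yet the result would carry an ITT label. Either way the text needs a change.

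*A reader might infer that most 48-month values would be carried forward.* The documents do not support that in general. The figure of 2900 is a ceiling, CIP 11.2 now moves to termination early, and at N = 1000 slightly more than half could be real.

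*A reader might infer that no phase 2 patient could reach 48 months on any schedule.* That rests on the June 2018 date. On the nominal two-year phase 1, phase 2 would start 50 months before the end, and the first two months of entrants could just get there. The documented date takes precedence over that schedule.

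*A reader might infer that carrying forward generally favours a false finding of no harm.* That is too strong. Early harm that fades is not diluted in this way, and with linear harm at N = 2900 the added patients offset the shrinkage in the test.

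*The stakes are limited.* CIP 7.3 sets no hypothesis for this endpoint, no margin is given, and 6- and 24-month tests are already planned. This is fair: the primary analysis is untouched.

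**Conclusion.** The point holds in this form. By the plan's calendar, a real 48-month WHO-5 score requires enrolment by about October 2017, and patients enrolled after the June 2018 announcement stop at 36 months at most. On the natural reading, SAP 24 fills the gap with earlier scores and tests them as 48-month scores on the whole ITT set.

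The size depends on an enrolment total that the documents do not give. Under the stated assumptions, real scores exist for about 18% of patients at N = 2900 and 52% at N = 1000, and the estimate of a linearly growing difference keeps about 45–53% and 69–73% of its size respectively. A marked loss of power follows only for late-onset harm. The change should be made before the final analysis; it concerns a secondary endpoint and how its result is labelled.

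**What to change.** In SAP chapter 24:

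1. Do not carry a WHO-5 score forward to a call date after the patient's own study termination or the formal end of the study.
2. Run the 48-month and 48-minus-6-month tests only in patients whose enrolment date is at least 48 months before formal study termination, and label the result as the early-enrolled cohort. Apply the same rule with 24 months to the 24-month and 24-minus-6-month tests. Count from enrolment, because CIP 9.6 schedules the calls from there; counting from index discharge could drop patients who have an observed 48-month score.
3. Report the number of observed scores per arm and visit.
4. Replace in-hospital with telephone follow-up in both sections numbered 24.3.

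Base the well-being statement for the whole ITT set on the 6-month comparison, and report later visits for patients with enough potential follow-up. The 12-month visit is less safe for this purpose: if entry ran to month 68, about 11–14% of 2900 patients could not reach it.

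The cost is SAP wording and a date filter in the program, with no new data. The filter uses only enrolment dates and one common end date, so it applies equally to both arms. The downside is a smaller 48-month sample, about 520 under the assumptions above, and a wider interval there.
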